6.1.13 Week 18 (Day 126 \pm 2 days Dose 10)

- Prior to dosing:
 - C-SSRS

CONFIDENTIAL

- Blood samples for routine safety
- 12-lead ECG
- Abbreviated Physical exam
- Vital signs prior to infusion, then at 30(\pm 5), 60(\pm 5) and 90(\pm 5) minutes from start of the infusion
- *Dosing by IV infusion*
- Adverse events and concomitant medications

6.1.14 Week 20 (Day 140 \pm 2 days Dose 11)

- Prior to dosing:
 - SIB
 - MMSE-2
 - ADCS-ADL-Sev
 - NPI
- Vital signs prior to infusion, then at 30(\pm 5), 60(\pm 5) and 90(\pm 5) minutes from start of the infusion
- *Dosing by IV infusion*
- Adverse events and concomitant medications

6.1.15 Week 22 (Day 154 \pm 2 days Dose 12)

- Vital signs prior to infusion, then at 30(\pm 5), 60(\pm 5) and 90(\pm 5) minutes from start of the infusion
- *Dosing by IV infusion*
- Adverse events and concomitant medications

6.1.16 Week 24 (Day 168 \pm 2 days Dose 13)

- Prior to dosing:
 - SIB
 - MMSE-2

CONFIDENTIAL

-
- ADCS-ADL-Sev
 - NPI
 - Vital signs prior to infusion, then at 30(\pm 5), 60(\pm 5) and 90(\pm 5) minutes from start of the infusion
 - *Dosing by IV infusion*
 - Adverse events and concomitant medications

6.1.17 Week 26 (Day 182 \pm 2 days Dose 14)

- Prior to dosing:
 - C-SSRS
 - Blood samples for routine safety
 - 12-lead ECG
 - Abbreviated Physical exam
- Vital signs prior to infusion, then at 30(\pm 5), 60(\pm 5) and 90(\pm 5) minutes from start of the infusion
- *Dosing by IV infusion*
- Adverse events and concomitant medications

6.1.18 Week 28 (Day 196 \pm 2 days)

- SIB
- MMSE-2
- ADCS-ADL-Sev
- NPI
- Vital signs
- Adverse events and concomitant medications

6.1.19 Week 30 (Day 210 \pm 2 days)

- SIB

CONFIDENTIAL

-
- Vital signs
 - Adverse events and concomitant medications

6.1.20 Early Termination

- SIB
- MMSE-2
- ADCS-ADL-Sev
- NPI
- CSSRS
- Blood samples for routine safety
- PE
- Vital signs
- Adverse events and concomitant medications

6.1.21 Follow-up Visits

- SIB
- Vital signs
- Adverse events and concomitant medications

6.1.22 Early Treatment Discontinuation and Follow-up

If for any reason, the investigator, subject or caregiver decide to discontinue the study drug or withdraw consent from the study, the subject and caregiver should be encouraged to complete an early termination (ET) visit and follow-up visit(s) as below:

- ET visit:
 - If the subject is withdrawn from the study at or before Week 13, subject will not enter Treatment Period 2.
 - If possible, schedule ET visits for 30 days (+/-2 days) after the last study drug dose administration
 - The ET reason must be documented with as much detail as possible in the EDC and in the source documents.

CONFIDENTIAL

- Follow-up Visits: Despite discontinuation of the study drug dosing, subjects and caregivers should be encouraged to return for additional follow-up visits for the duration of the trial, in order to monitor for safety and any changes in cognition.
 - The follow-up visits should be scheduled to coincide with the cognitive assessment visits scheduled after the study drug discontinuation (i.e., weeks 5, 9, 13, 15, 20, 24, 28, 30).
 - The below assessments should be completed at all follow-up visits:
 - SIB
 - Vitals
 - Adverse Events
 - Concomitant medications
 - If the subject is willing to return for only one follow-up visit, please schedule this visit to occur approximately 30 days (+/-2 days) following the last study drug dosing.

6.2 Concomitant Medications

During the screening visit, the Caregiver will provide a history of prior medication use during the past 6 months and provide a list of currently used medications. All concomitant medications used should be recorded on the eCRF and in the source documents using the generic name for the drug. Assessment of concomitant medications will take place at each study visit. Any changes to chronic medications should be noted as well as new and discontinued medications.

Subjects taking allowed antidepressant medications may be enrolled in the study (see Appendix 1). The dose and dose regimen for these medications should be stabilized for at least 30 days prior to enrollment in the study. Every effort should be made to keep the dose and dose regimen of antidepressant medications stable throughout the study.

6.2.1 Medications for AD

Subjects taking FDA approved medications for the treatment of AD, **with the exception of memantine or any drug containing memantine**, may be enrolled in the study. The subject must be on a stable dose of permitted medications for at least 3 months prior to entry into the study and dose must not change during the study. Subjects may not initiate additional drugs for treatment of AD during the study other than the study drug.

6.2.2 Concomitant Medications for Management of Myalgia

Non-steroidal anti-inflammatory drugs such as ibuprofen and naproxen sodium are permitted. Use of acetaminophen as an analgesic is contraindicated as it has the ability to inhibit PKC activation.

6.2.3 Prohibited Medications

Memantine is prohibited. Subjects previously treated with memantine must stop treatment at least 90 days prior to initiation of study drug treatment. Treatment with other NMDA receptor antagonists such as but not limited to dextromethorphan (a cough suppressant), ketamine,

CONFIDENTIAL

phencyclidine (PCP), methoxetamine (MXE), nitrous oxide (N₂O) and the following synthetic opioids: penthidine, levorphanol, methadone, dextropropoxyphene, tramadol, and ketobemidone is prohibited and a 30-day washout period is required prior to initiation of study drug treatment.

High dose Vitamin E (> 400 IU / day), Valproic Acid and divalproex sodium are prohibited.

Gabapentin is prohibited.

If the PI determines that initiation of any of the prohibited medications is required to ensure the subject's safety, the medication may be initiated with the notification of the Medical Monitor and proper documentation of a protocol deviation. Other restricted concomitant medications are listed in Appendix 1.

7 ADVERSE EVENTS AND OTHER SAFETY EVALUATIONS

7.0 Definition of Adverse Events

An AE is any untoward medical occurrence associated with the use of a drug in humans, whether or not considered drug related. An AE (also referred to as an adverse experience) can be any unfavorable and unintended sign (e.g., clinically significant abnormal laboratory finding), symptom, or disease temporally associated with the use of a drug, without any judgment about causality.

The PI is responsible for obtaining information about all medical emergencies during the clinical study. The PI's contact information will be located in the body of the informed consent form (ICF) and subjects/caregivers will be encouraged to contact the PI or clinical site personnel during any clinical study-related emergency.

All adverse events spontaneously reported by the subject and/or caregiver in response to an open question or revealed by observation will be recorded during the study regardless of relationship to the study drug. All AEs will be monitored and recorded for the progress of the event until it resolves or reaches a clinically stable outcome. Adverse events that are not resolved at the time of database lock will be recorded as ongoing.

The AE and SAE reporting period starts from the time of consent to the last study visit.

7.1 Adverse Event of Special Interest - Myalgia

Myalgia has been reported as the dose limiting toxicity across the oncology studies. The incidence of myalgia appears to be dose dependent and cumulative. However, it has been reported in subjects receiving doses as low as 5µg/m². The myalgia has been investigated in some studies but not all. No increase in muscle enzymes were found in the cases investigated. EMG was abnormal in one subject who received 65µg/m² and suggested a patchy myositis. An MRI done in another subject was normal.

CONFIDENTIAL

For all cases of myalgia despite the severity, a narrative will be created documenting onset, severity, treatment and outcome. Muscle enzymes, CPK, will be collected for all cases and compared to baseline values. Additional investigations are at the discretion of the investigator.

7.2 Definition of Serious Adverse Event

An SAE is any untoward medical occurrence that fulfills any of the following criteria:

- Results in death (fatal)
 - Is life threatening (an event is considered “life threatening” if, in the view of either the investigator or sponsor, its occurrence placed the subject at immediate risk of death. It does not include an AE that, had it occurred in a more severe form, might have caused death).
 - Requires in-patient hospitalization or prolongation of existing hospitalization
 - Results in a persistent or significant disability/incapacity
 - Is a congenital anomaly/birth defect
- or
- Is an important medical event (events that may not result in death, be immediately life threatening or require hospitalization; may be considered serious when based upon appropriate medical judgment, they jeopardize the subject and may require medical or surgical intervention to prevent any of the outcomes listed above. Examples include; allergic bronchospasm requiring intensive treatment in an emergency room or at home, convulsions that do not result in hospitalization, or the development of drug dependency or drug abuse.

The following situations may not, by themselves, constitute sufficient grounds to be considered as an SAE:

- Hospitalization solely for a diagnostic purpose, even if related to an AE,
- Elective hospitalization for an intervention planned before the subject enrollment in the study
- Admission to a day care facility or sleeping laboratory

7.3 Assessment of Intensity

Severity is a clinical determination of the intensity of an AE and will be determined by the PI based on the following classification criteria for all AEs occurring during the clinical study:

Mild - Awareness of signs or symptom, but easily tolerated, may require additional therapy

Moderate - Discomfort, enough to cause interference with usual activity and to require intervention or additional therapies

Severe - Incapacitating with inability to work or perform usual activity

CONFIDENTIAL

Note: It should be noted that a severe AE need not be serious in nature and that an SAE is not, by definition, severe. Regardless of intensity, all SAEs and significant events must be reported.

7.4 Relationship to Study Drug

The causal relationship between the investigational drug and each AE will be determined by the PI based on his/her medical judgment in consideration of all relevant factors, including pattern of reaction, temporal relationship, positive, concomitant medication, co-existing diseases, and relevant medical history. The PI will classify every AE according to its relationship to study drug or trial-related procedures. The categories according to World Health Organization guidelines are listed in the following Table

7.5 Table 2 Relationship of AE to Study Drug or Trial-Related Procedures

Rating	Classification	Definition
1	Probable	An AE that: 
 • Occurs at a reasonable time interval after administration of the study drug; • Follows a known response pattern to the study drug and; • Cannot be reasonably explained by the known characteristics of the subject's clinical state or by other therapies.
2	Possible	An AE that: 
 • Occurs at a reasonable time interval after administration of the study drug; • Follows a known response pattern to the study drug, but; • Could have been produced by the subject's clinical state or by other therapies. •
3	Unlikely*	
 • An AE for which sufficient information exists to indicate that the etiology is unrelated to the study drug; • Another etiology is specified.

*If the AE is classified as unlikely, the PI should provide a likely cause, other illness, concomitant medication, or other.

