7.5.1 Unexpected Adverse Event

An AE is considered “unexpected” if it is not listed in the Investigator’s Brochure (IB) or is not listed at the specificity or severity that has been observed. Unexpected refers to AEs that are mentioned in the IB as occurring with a class of drugs or as anticipated from the pharmacological properties of the drug, but are not specifically mentioned as occurring with the particular drug

CONFIDENTIAL

under investigation. However, an event that is more specific or more severe than described in the IB will be considered unexpected.

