7.6.2 Reporting to Regulatory Authorities

The PI, or designee, is responsible for informing the Institutional Review Board (IRB) of any unexpected SAEs, as well as any additional SAEs according to the IRB's policy.

Any SAE that is serious, suspected to be related to investigational study drug and unexpected (SUSAR), will be promptly reported to regulatory authorities by the Sponsor according to expedited reporting requirements. Subsequent relevant information after the initial submission of the (IND) Safety Report to the regulatory authorities will be submitted in a follow-up IND Safety Report to the regulatory authorities in the expedited period by the Sponsor.

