9.8.1 Adverse Events

Adverse events will be coded using the most recent version of Medical Dictionary for Regulatory Activities (MedDRA). Treatment Emergent AE's (TEAE) are defined as events with an onset on or after the first randomized treatment. TEAEs will be summarized by treatment group, System Organ Class, and preferred term. The following TEAE summaries will be provided:

- Overall (*i.e.*, regardless of severity or relationship to treatment)
- By severity grade (mild, moderate, severe, life threatening or death for SAEs)
- By relationship to clinical trial treatment (definitely related, probably related, possibly related, unlikely related, unrelated)

Unless otherwise specified, at each level of subject summarization, a subject will be counted only once. If there is more than one occurrence of an event, the event of the worst severity or the worst-case relationship category will be summarized.

In addition, separate summaries of serious adverse events, and adverse events resulting in discontinuation of study treatment will be presented.

AEs leading to premature discontinuation of clinical trial treatment, AEs that lead to study discontinuation, AEs that lead to death and Serious Adverse Events (SAEs) will also be summarized by treatment group and relationship.

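### Table 2 has no causality rating for a plausibly timed new type of reaction with no established other cause, because both related ratings require a known response pattern

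*Protocol*

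**What the plan says.** Protocol 7.5, Table 2, gives three ratings, each with joint criteria:

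- **Probable**: reasonable timing; "Follows a known response pattern to the study drug and" no other reasonable explanation.
- **Possible**: reasonable timing; "Follows a known response pattern to the study drug, but" the patient's condition or another therapy might have caused it.
- **Unlikely**: "An AE for which sufficient information exists to indicate that the etiology is unrelated to the study drug", with the second criterion "Another etiology is specified". A footnote asks the investigator to supply a likely cause.

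Protocol 7.4 introduces this table by telling the investigator to judge causality "based on his/her medical judgment in consideration of all relevant factors, including pattern of reaction, temporal relationship" and several others.

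The rating is used in these places:

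- Protocol 7.6.2, expedited reporting: "Any SAE that is serious, suspected to be related to investigational study drug and unexpected (SUSAR), will be promptly reported". Section 7.5.1 counts an event as unexpected if it is absent from the Investigator's Brochure or "is not listed at the specificity or severity that has been observed".
- Protocol 7.6 and 7.6.1: late SAEs (more than 30 days after the last dose, or after the 30-day safety visit) are collected only if the investigator regards them as drug-related.
- Protocol 9.8.1: TEAEs summarised under five labels, "definitely related, probably related, possibly related, unlikely related, unrelated".
- SAP 6.12.1: relationship is taken from the CRF causality variable, and a missing value is set to the maximum relationship. SAP section 8 gives the DSMB TEAE, serious TEAE and special-interest tables by relationship.

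**The concern.** A causality scale should have a place for an event that starts at a plausible time after dosing, looks like nothing seen before with the drug, and has no proven other cause. That is how a new toxicity first appears. Table 2 makes prior knowledge of the reaction a condition of both ratings that imply a drug relationship, and it reserves the third for events already attributed to something else.

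This matters here because experience in Alzheimer's disease is limited. The protocol says so itself in section 4.2 when it declines to rule out amyloid-related imaging abnormalities. The earlier Alzheimer's trials it describes gave one dose or seven, and this one schedules 14. At stake are the by-relationship tables, the route by which new serious reactions are recognised as suspected, and the collection of late SAEs.

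**Working it through.** No sample size, power or rate bears on this point. The check is whether the criteria cover the cases, followed by a trace of the rating through the plan.

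**1. Coverage of Table 2.** Take an event with plausible timing and cross the pattern (known, new) with the state of an alternative cause (none, only possible, shown and specified): 2 × 3 = 6 combinations.

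| Alternative cause | Known pattern | New pattern |
|---|---|---|
| None | Probable | no rating fits |
| Only possible | Possible | no rating fits |
| Shown and specified | Unlikely | Unlikely |

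Both empty cells are in the new-pattern column. Probable and Possible fail there for want of a known pattern. Unlikely fails for want of evidence against the drug and of a specified cause. So for new-pattern events two of three situations have no rating.

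**2. Conflict with 7.4.** Section 7.4 lists pattern of reaction beside timing, concomitant medication, co-existing disease and history, all to be weighed. Table 2, which the same paragraph introduces as the classification for every AE, turns pattern into a condition. An investigator cannot follow both for an event in an empty cell.

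**3. What happens to such an event in the analysis.** It depends on what the site enters:

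- *Unlikely*: the event leaves the related counts in the CSR and DSMB tables.
- *Left blank*: SAP 6.12.1 counts it at maximum relationship, the opposite direction. But 7.6 requires relationship to be recorded for each AE and 12.2 queries omissions, so a blank is not a planned outcome.
- *Possible or Probable on judgment under 7.4*: it is counted, against the letter of Table 2.

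In every case it stays in the overall TEAE and serious TEAE tables.

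**4. Expedited reporting.** Section 7.6.1 requires all SAEs to be reported within 24 hours whatever their rating, and a pharmacovigilance physician reviews relationship and expectedness. The trigger in 7.6.2 does not cite Table 2. An SAE rated Unlikely within the 30-day window therefore still reaches someone who can call it suspected, but recognition then depends on that review alone.

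**5. Late SAEs.** Here the investigator's view decides whether the event is collected at all. For a completer the nominal last visit (Week 30, Day 210) falls 210 − 182 = 28 days after Dose 14, inside the window. For a subject whose last infusion is Dose 7 (Day 77) and who stays in follow-up to Week 30 under 6.1.22, it falls 210 − 77 = 133 days after the last dose, so 133 − 30 = 103 days lie outside the window. Section 7.0, by contrast, runs AE and SAE reporting to the last study visit, and the two rules need reconciling.

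**6. Labels.** Section 9.8.1 has five categories and Table 2 has three: 5 − 3 = 2 categories (definitely related, unrelated) have no definition at the point of rating.

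**The case against.** The strongest reply is that the plan has enough safeguards to make this a matter of wording. SAEs within 30 days are reported regardless of causality and their relationship is reviewed again. Section 7.6 also asks sites to pass on unusual or potentially drug-related safety information even after a subject finishes. Section 7.4 leaves causality to medical judgment. All-causality tables by arm, which in a placebo-controlled trial are the natural place to see a new toxicity, remain complete, and the DSMB receives them with full TEAE listings.

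Most of this stands, and it rules out several stronger readings that a reader might infer:

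- *That new reactions drop out of SUSAR reporting.* They do not do so automatically, for the reasons in step 4.
- *That only a worse or more specific form of a known reaction could be a SUSAR.* A known response pattern is not the same as a listing in the Investigator's Brochure. Section 7.5.1 treats events anticipated from the drug's pharmacology, but not listed for it, as unexpected. Such an event might fit a known pattern.
- *That sites can only choose Unlikely.* A site applying the definitions could not choose it for an unexplained event.
- *That the previous trial shows the harm.* In NTRP101-203 all 15 SAEs were rated unlikely related, but they are pooled over both arms, and nothing says they were new, unexplained or rated on this scale. In NTRP101-202 four SAEs, one a seizure, were judged possibly or probably related.

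The safeguards do not reach everything. The documents describe no second causality review for non-serious AEs, whose ratings pass from the CRF into the tables. The late-SAE rule operates before any sponsor review.

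**Conclusion.** The gap in Table 2 is real on its own wording: a plausibly timed reaction of a new type, without an established other cause, has no valid rating, and the table conflicts with 7.4. Two of the five categories in 9.8.1 are also undefined in Table 2.

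The consequences are conditional. If sites resolve the gap by entering Unlikely, related-AE counts are too low for new toxicities, SUSAR identification within the 30-day window rests on the sponsor's review, and later SAEs may not be collected. That default is an assumption, because the eCRF causality options are not shown. How many events would be affected cannot be estimated from the documents. All-causality TEAE and SAE comparisons are not affected. The point merits correction because a stated rule feeds reported tables and is cheap to repair, not because events disappear from the trial.

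**What to change.** In Table 2, make a known response pattern supportive and not mandatory, and let the alternative-cause criterion separate the ratings:

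- **Probable**: reasonable timing, and not reasonably explained by other causes.
- **Possible**: reasonable timing, but other causes could also explain it.
- **Unlikely**: another etiology indicated and specified, or timing not plausible.

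This fills both empty cells in step 1. Removing the pattern criterion from Possible without this separation would let a well-timed event with no other cause meet both Possible and Probable. The timing clause in Unlikely gives a rating to an implausibly timed event with no documented cause.

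Use the same set of ratings in Table 2, the eCRF, Protocol 9.8.1 and SAP 6.12.1, and state in 7.6.2 which ratings count as suspected. Reconcile the SAE collection periods in 7.0, 7.6 and 7.6.1.

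The cost is a wording amendment and updated eCRF options and completion guidance. Somewhat more events will be rated possible or probable in both arms, and a few more expedited reports will follow.

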7.5.1 Unexpected Adverse Event

An AE is considered “unexpected” if it is not listed in the Investigator’s Brochure (IB) or is not listed at the specificity or severity that has been observed. Unexpected refers to AEs that are mentioned in the IB as occurring with a class of drugs or as anticipated from the pharmacological properties of the drug, but are not specifically mentioned as occurring with the particular drug

CONFIDENTIAL

under investigation. However, an event that is more specific or more severe than described in the IB will be considered unexpected.

